Patients with advanced cancer experience multiple physical and psychosocial symptoms, including pain, fatigue, weight loss, lack of appetite, nausea, emesis, anxiety, dyspnea, and confusion (1-3). The causes of these symptoms can be related to the neoplasm and complications of treatments such as surgery, chemotherapy and/or radiation; the symptoms significantly affect the patients' quality of life (4). The particularly distressing symptom of chronic nausea may be present in over 60% of patients with advanced cancer (5).

Nausea is a subjective, difficult-to-describe, sick or queasy sensation, usually perceived as being in the stomach; it is sometimes followed by emesis (6). The experience of nausea is difficult to describe in individual people because it is a subjective sensation. Nausea has been assumed to be the conscious awareness of unusual sensations in the "vomiting center" of the brainstem, but the existence of such a center and its relationship to nausea remain controversial (6). Nausea and emesis are not always directly associated with each other. One can experience nausea without emesis and one can have sudden emesis without nausea.

The etiology of chronic nausea in advanced cancer patients is multifactorial. Etiologies include medications such as opioids, delayed gastric emptying, mechanical bowel obstruction, increased intracranial pressure, vestibular dysfunction, metabolic issues, and/or cortical effects such as anxiety or depression (2). Delayed gastric emptying and partial bowel obstruction may account for a significant cause of chronic nausea (2,7). Chronic nausea may persist for a significant time and cause complications such as anorexia and fatigue, impaired performance status, and diminished quality of life (2).

A number of palliative care studies have considered various empirical treatments of chronic nausea with limited success (8). One palliative care group has recommended metoclopramide and haloperidol for use as initial treatment for nausea and vomiting in advanced cancer, with olanzapine as second line therapy, and ondansetron as third line therapy (9). However, in 2013, the European Medicines Agency's Committee on Medical Products for Human Use recommended that the use of metoclopramide be limited due to serious neurological side effects (10).

Davis et al. (11) have reported a systematic review of the treatment of nausea and/or vomiting in cancer unrelated to chemotherapy or radiation. Ninety-three articles were found with fourteen of them being randomized clinical trials, most of low quality. Metoclopramide was felt to have had modest evidence for efficacy, but there was no evidence that multiple antiemetics or any specific antiemetic had significant efficacy based on the current data in the literature. The conclusion of the review was that antiemetic recommendations for chronic nausea in cancer patients are based on weak to moderate evidence at best, and prospective randomized trials of single antiemetics are needed to properly establish evidence-based guidelines.

Further evidence that new agents are needed to treat chronic nausea in cancer patients came from a recent trial demonstrating that dexamethasone was not superior to placebo in the management of chronic nausea in patients with advanced cancer in whom metoclopramide was not effective (12).

Based on these data and on a recent phase III study of the efficacy of olanzapine versus metoclopramide for the treatment of breakthrough chemotherapy-induced nausea and vomiting (CINV) (13), olanzapine appears to be a very reasonable candidate for study for the treatment of chronic nausea in patients with cancer. Olanzapine, an atypical antipsychotic agent of the thiobenzodiazepine class, was approved by the FDA for the treatment of the manifestations of psychotic disorders in 1996 (14,15) with a generic formulation becoming available in 2011. This drug blocks multiple neurotransmitter receptors including dopaminergic (D₁, D₂, D₃, D₄ brain receptors), serotonergic (5-HT_{2a}, 5-HT_{2c}, 5-HT₃, 5-HT₆ receptors), catecholaminergic (alpha₁ adrenergic receptors), acetylcholinergic (muscarinic receptors), and histaminergic (H₁ receptors) (16). Olanzapine has five times the affinity for 5-HT₂ receptors than for D₂ receptors (17). The effect of olanzapine on the serotonin-mediated 5-HT_{2c} receptor as well as other dopamine and serotonin receptors may explain, in part, its efficacy in alleviating nausea and vomiting.

A benefit of olanzapine is that it is not a cytochrome P450 inhibitor and thus appears to have fewer drug interactions than many other drugs (16). Common side effects are sedation and weight gain (18,19), and the weight gain can lead to diabetes mellitus when given for a period of greater than six months (20).

There have been case reports on the use of olanzapine as an anti-nausea agent for oncology conditions other than CINV (21-27). A patient with leukemia reported a significant improvement in chronic nausea with the use of olanzapine (25) and, in six patients receiving palliative care, olanzapine was reported to be effective for intractable nausea due to opioids, neoplasm, and/or medications (21). In another report, olanzapine was effective in controlling refractory nausea and vomiting in two patients with advanced cancer (26). Olanzapine was also reported to be effective in controlling opioid-induced nausea (27).

Bowel obstruction is one of the most common complications in patients with advanced cancer either due to the ingestion of pain medications, large or small intestinal dysfunction, or other tumor-induced issues (2,5). A retrospective study, carried out on a palliative care unit, demonstrated that, in 18 of 20 patients with incomplete bowel obstruction, the use of olanzapine led to a significant decrease in the average intensity score of nausea, suggesting a role for olanzapine in the symptom relief in patients with incomplete bowel obstruction (28).

The National Cancer Institute recently approved a multi-institutional phase III clinical trial (Alliance A221301) for the prevention of CINV in patients receiving highly emetogenic chemotherapy using olanzapine plus standard antiemetics compared to placebo plus standard antiemetics (29). The trial was based on substantial evidence that this drug is helpful for preventing chemotherapy-induced nausea and vomiting (30-34) and for treating nausea/vomiting that had occurred as a result of chemotherapy (13). This randomized, double-blind, phase III trial was performed in chemotherapy naïve patients receiving cisplatin, ≥ 70 mg/m², or cyclophosphamide-anthracycline-based chemotherapy, comparing olanzapine (OLN) to placebo (PLA) in combination with aprepitant (APR), a 5-HT₃ receptor antagonist (5-HT₃), and dexamethasone (DEX). The OLN regimen was 10 mg of oral OLN, 125 mg oral APR, a 5-HT₃, and oral DEX 12 mg pre-chemotherapy, day 1, and 10 mg/day of oral OLN on days 2-4 post-chemotherapy, 80 mg oral APR, days 2,3 post chemotherapy, and 8 mg oral DEX , days 2-4 post chemotherapy. The PLA regimen was oral placebo, day 1, and oral placebo on days 2-4 post chemotherapy, with the APR, 5-HT₃, and DEX pre and post-chemotherapy being the same as in the OLN regimen. Fosaprepitant (150 mg IV), day 1 could be substituted for the oral aprepitant. Palonosetron, ondansetron, or granisetron were the permitted 5-HT₃ options. Nausea was measured on a 0-10 visual analogue scale, with 0 being no nausea at all and 10 being nausea as bad as it can be.

Four hundred one patients were enrolled with 380 patients evaluable (192 patients receiving the OLN regimen and 188 patients receiving the PLA regimen). The proportion of patients with no nausea was significantly improved for the OLN regimen compared to the PLA regimen for the acute period (24h post-chemotherapy) (74% vs. 45%, p=0.002), for the delayed period (25 to 120 hours post-chemotherapy) (42% vs. 25%, p=0.002), and for the overall period (0-120 h) (37% vs. 22%, p=0.002). Complete response (CR) (no emesis, no rescue medications) was significantly improved in OLN compared to PLA patients for the acute (86% vs. 65%, p<0.001), the delayed (67% vs. 52%, p=0.007), and the overall periods (64% vs. 41%, p<0.001). There were no Grade 3 or 4 toxicities. No nausea, the primary endpoint, and complete response, a secondary endpoint, were significantly improved with OLN compared to PLA (29).

Based on the above, it appears that olanzapine has significant potential for use in the prevention and treatment of nausea in a palliative care setting including in patients with opioid-induced nausea. Due to its mechanism of action, blocking multiple neurotransmitter receptors, it can be used as a single agent; due to its long half-life, it can be given as once-daily dosing. Therefore, patient compliance should be reasonable.

The purpose of the current proposed study is to evaluate the use of olanzapine for the treatment of cancer patients with chronic nausea and/or emesis unrelated to chemotherapy or radiation in a randomized placebo-controlled pilot clinical trial.

Much thought was given to the appropriate control arm for this study. While we considered choosing a single comparator (such as haloperidol or metoclopramide), there was no established agent to recommend and patients may have already tried one that we might have chosen as a single comparator. There have been multiple recent treatment trials that have used physician's choice as a control, with good accrual and good results (35-37) and we considered this option. This topic regarding a control arm was

discussed in detail with community and academic investigators at various Alliance committees and meetings. In the end, it was decided to use a placebo arm in the study since nausea can be subjective and vary under multiple conditions and with different patients. If a patient has persistent nausea or vomiting 2-3 days after study enrollment, then they can opt out of the study, while still blinded to the treatment arm. This will allow this to be a treatment outcome of interest (with the hypothesis that more placebo patients will drop out than active treatment patients).

III. Study Objectives

Primary: To conduct a pilot trial to estimate the proportion of cancer patients with an improvement in chronic nausea, unrelated to chemotherapy or radiation after treatment, with olanzapine versus a placebo.
Secondary:

- To evaluate toxicity associated with olanzapine in the current situation
- To evaluate the number of patients in each study arm who stop therapy prior to 5 days
- To evaluate the utility of this trial design, including the defined patient eligibility, for potential use in a phase III trial, assuming that these data are promising from the current trial

IV. Study Plan

Patient Selection

Eligibility Criteria

Eligible patients will:

- Be at least 18 years of age,
- Have histologically or cytologically-confirmed malignant disease in an advanced incurable stage
- Have not received chemotherapy or radiation for ≥ 14 days (advanced cancer patients receiving hormonal therapy or targeted therapy that does not come with a recommendation for prophylactic anti-emetic therapy are eligible)
- Have chronic nausea that has been present for at least one week (worst daily score ≥ 3 , 0-10 visual analogue scale) or vomiting at least five times over past one week
- Have serum creatinine ≤ 2.0 mg/dl and SGOT or SGPT ≤ 3 times upper limits of normal ≤ 120 days prior to registration.
- ANC ≥ 1500 mm 3 < 120 days prior to registration
- Not be receiving treatment with another antipsychotic agent such as risperidone, quetiapine, clozapine, phenothiazine or butyrophenone for ≤ 30 days prior to registration or planned during protocol therapy (patients may have received prochlorperazine and other phenothiazines as prior anti-emetic therapy)
- Not have: concurrent use of ethyl; severe cognitive compromise; known history of CNS disease (e.g. brain metastases, seizure disorder); concurrent use of amifostine, concurrent abdominal radiotherapy; concurrent use of quinolone antibiotic therapy; chronic alcoholism (as determined by the investigator); known hypersensitivity to olanzapine; known cardiac arrhythmia, uncontrolled congestive heart failure or acute myocardial infarction within the previous six months; history of uncontrolled diabetes mellitus (stable insulin dose and/or stable oral hypoglycemic agent permitted); or have planned chemotherapy or radiation during the 7 days following study initiation.
- In addition, women of childbearing potential must consent to use adequate contraception throughout protocol therapy; females of childbearing potential must have a negative urine pregnancy test ≤ 7 days prior to registration.

This clinical trial can fulfill its objectives only if patients appropriate for this trial are enrolled. All relevant medical and other considerations should be taken into account when deciding whether this protocol is appropriate for a particular patient. Physicians

should consider the risks and benefits of any therapy, and therefore only enroll patients for whom this treatment is appropriate.

Although they will not be considered formal eligibility (exclusion) criteria, physicians should recognize that the following may seriously increase the risk to the patient entering this protocol:

- Psychiatric illness that would prevent the patient from giving informed consent.
- Medical condition such as uncontrolled infection (including HIV), uncontrolled diabetes mellitus or cardiac disease which, in the opinion of the treating physician, would make this protocol unreasonably hazardous for the patient.
- Patients who cannot swallow oral formulations of the agent(s).

In addition:

- Women of reproductive potential should agree to use an appropriate method of birth control throughout their participation in this study due to the teratogenic potential of the therapy utilized in this trial.

Patient Registration/Randomization

Patient registration can occur after pre-treatment evaluation is complete, eligibility criteria have been met, and the patient must has signed the informed consent.

Contact the Study Chair or Registration Specialist who will have the patient registered into the study and have the patient randomized. After the treatment assignment has been ascertained, the patient's study medication code number will be used to confirm the registration.

To ensure both the patient and the medical professionals who care for the patient are blinded to the identity of the treatment assignment, the Registration Specialist will follow a double-blinding procedure. The pharmacist or designated contact person at the treating site will maintain records that indicate the identity of the patient and their corresponding study medication code number.

Study Calendar

	Prior to Registration	Days 1-7	Day 8
Tests & Observations			
History and physical, weight, ECOG PS, and complete demographics (Appendix I)	X X		
Nurse phone call (record per Appendix IV)		X ³	X ³
Baseline and Daily Questionnaire and Vomiting Assessment (Appendix II)	X ¹	X ²	X ²
FACT-G (Quality of Life) (Appendix III)	X		X
Well Being Assessment (Patient and Investigator)(Appendix II)	X		X
Serum or Urine HCG	X ⁴		
Creatinine, SGOT,SGPT, ANC	X ⁵		

- 1 To be completed by patient after registration and prior to treatment.
- 2 Patient to complete daily on days 1-8.
- 3 Nurse/Research Coordinator will contact each patient each day (days 2-8) to remind the patient to complete forms, answer questions, and to query adverse events. Please try to call the patient around the same time of day as the study drug was given on day 1 (+/- 1 hour).
- 4 For women of childbearing potential, must be done \leq 7 days prior to registration.
- 5 To be completed \leq 120 days prior to registration.

Data Collection and Submission

The data collection will be via forms completed by the patient, the investigator, and the research nurse on days 1 to 8 during the study. The forms will be submitted via fax or e-mail to the Study Chair.

Treatment Plan/Intervention

Protocol treatment is to begin \leq 14 days of registration. Protocol therapy will be instituted daily for seven days. Patients will be permitted to take rescue therapy (treating investigator's choice) anytime during the seven day treatment period based on the evaluation of the treating investigator for nausea and/or emesis/retching, based on clinical circumstances.

Definitions of Deviations in Protocol Performance

Major Deviations

A "major deviation" is a situation in which patient safety or outcome is compromised.

Minor Deviations

A "minor deviation" is a discrepancy from the protocol that is not of sufficient magnitude to prevent adequate evaluation of the patient and does not cause the patient to be excluded from the statistical evaluation.

Data Collection and Forms

The patient will complete the Baseline and Daily Questionnaire and Vomiting Assessment on day one prior to the start of treatment and on days 2-8 at the same time of day as the protocol therapy.

Dose and Treatment Modifications, Unblinding

Ancillary therapy, concomitant medications, and supportive care

Patients should receive full supportive care while on this study, as determined to be appropriate by their attending clinicians.

Dose Modifications

If the patient experiences a significant adverse event (per patient and physician discretion) felt to potentially be related to the study product (olanzapine/placebo), then the study product should be stopped and this should be recorded.

Unblinding Procedures

Protocol-specified Unblinding:

Trial participants may be unblinded upon completion of protocol therapy and submission of all of their questionnaire results. Any potential toxicity of the study agent (olanzapine/placebo) needs to be determined and recorded prior to unblinding of the investigator and/or patient. Contact the Study Chair during regular business hours.

Emergency Unblinding Procedures:

A trial participant's treatment assignment can be unblinded in emergent situations with the approval of the Study Chair (or designee) only if unblinding would influence management of the situation, e.g., if a child has swallowed a vial of pills.

Adverse Events

The prompt reporting of adverse events is the responsibility of each investigator engaged in clinical research, as required by Federal Regulations. Adverse events must be described and graded using the terminology and grading categories defined in the NCI's Common Terminology Criteria for Adverse Events (CTCAE), Version 4.0. The CTCAE is available at http://ctep.cancer.gov/protocolDevelopment/electronic_applications/ctc.htm. Attribution to protocol treatment for each adverse event must be determined by the investigator and reported on the required forms, using the codes provided.

Routine adverse event reporting

Adverse event data collection and reporting, which are required as part of every clinical trial are done to ensure the safety of patients enrolled in the studies as well as those who will enroll in future studies using similar agents.

Solicited adverse events: None, other than those collected by the daily patient completed questionnaire, which will include drowsiness.

Expedited adverse event reporting

Investigators are required by Federal Regulations to report serious adverse events as defined below. Investigators are required to notify the Study Chair, and their Institutional Review Board if a patient has an adverse event requiring expedited reporting. All such events must be reported in an expedited manner using the CTEP Adverse Event Reporting System (CTEP-AERS). The descriptions and grading scales found in the NCI Common Terminology Criteria for Adverse Events (CTCAE) version 4 will be utilized for reporting. The CTCAE is identified and located on the CTEP website at: http://ctep.cancer.gov/protocolDevelopment/electronic_applications/ctc.htm. All treatment areas should have access to a copy of the CTCAE version 4.0. A copy can be downloaded from the CTEP website <http://ctep.cancer.gov>.

Be sure to read this entire protocol section, as requirements are described in both the table and bullet points following the table. In the case of a conflict, the additional instructions or exclusions supersede the table.

Informed Consent

All patients must give written informed consent, and the study must be approved by the institutional review committees of each participating site (Appendix V).

Study Design and Treatment Regimen

All patients eligible for the study will be randomized to receive olanzapine (5.0 mg/day, orally, days 1 to 7) or a placebo (orally, days 1 to 7). Randomization will be stratified by gender.

The protocol dose of olanzapine was determined from the various studies in the literature (13, 21-28, 30-34). Although 10 mg/day for four days has been the commonly used olanzapine dose, in combination with other antiemetics, in studies for the prevention of chemotherapy-induced nausea and vomiting (30-34), a 5 mg/day dose was chosen for this pilot trial as this lower dose has been used in case reports for the treatment of chronic nausea in the literature (21-28) and by Alliance Symptom Intervention committee members in clinical practice, with perceived efficacy and with little to no toxicity.

The study treatment will be 7 days and study duration will be 8 days. Patients will be permitted to stop the assigned antiemetic treatment at any time during the 7 days and change to an alternative antiemetic treatment (any rescue therapy as determined by the patient's physician) if the patient has persistent nausea and/or emesis/retching that has not responded to the assigned antiemetic treatment. Patients may request rescue or a patient's physician may determine rescue is necessary at any time during the 7 day period. Patients will not necessarily be taken off study after rescue therapy is initiated.

When the patient has completed their study period (i.e., 8 days), including all required questionnaires, they can be unblinded. **If they were on the placebo, we will give them a supply of olanzapine to try (assuming that they want to try this).**

If a patient has continued substantial nausea and/or vomiting after being on the study for 2 days, they can choose to stop the study. They can be unblinded after they and the nurse have completed all the study questionnaires (so that more accurate attribution can be made prior to unblinding).

Study Visits and Assessment Procedures

In the pre-study period, all pertinent demographics (e.g. age, gender, height, weight) and appropriate medical data (e.g. site and stage of disease, ECOG PS, laboratory values, medications and present therapies including present oncologic therapy) will be recorded. The investigator will be asked to record their best estimate of the primary clinical etiology (medications (opioids), delayed gastric emptying, partial bowel obstruction, vestibular dysfunction, metabolic issues, anxiety, and depression) of the chronic nausea prior to study entry.

Patient-reported outcomes (PROs) will be the primary means for measuring the study endpoints. The major end points of the study will be nausea (0-10, visual analogue scale) and /or episodes of vomiting, day 1 pre-treatment and days 2-8 post treatment initiation.

Extensive reviews of the assessment of chronic nausea and emesis in patients with advanced cancer have suggested the use of a visual analogue and a categorical scale to assess key symptoms (appetite, nausea, fatigue, pain), vomiting, and quality of life (11, 13, 29-34, 38). After patients give informed consent and after demographic information is obtained (Appendix I), patients will have a baseline assessment which will include assessment of symptom intensity (appetite, nausea, fatigue, sedation, pain) and vomiting in the previous 24 hours (Appendix II), and assessment of quality of life (QOL) (Appendix III). The five symptoms will be measured on a visual analogue scale (0-10) (0 = symptom absent, 10 = worst possible symptom). The number of vomiting episodes in the preceding 24 hours will be recorded. Well-being will be estimated on a 0-10 numerical scale (0 = best possible, 10 worst possible) (Appendix II). QOL will be measured by the Functional Assessment of Cancer Therapy-General (FACT-G) instrument (Appendix III), a well-established QOL instrument consisting of 27 questions grouped into four domains (39).

The study duration for the primary endpoint will be 8 days. Each day, the patients will estimate the intensity of their appetite, nausea, fatigue, sedation, and pain using the numerical visual analogue scale, and record the number of vomiting episodes in the previous 24 hours. The patient will also record the use of the daily dose of the study drug in a medication log as well as the use of any rescue medications.

On day 8, the patient will complete the last daily dairy (to capture day 7 data) and will estimate the quality of life with the FACT-G instrument, and both the patient and the investigator will assess the patients' well-being, using the 0-10 numerical scale.

The patient will be asked to complete the forms at approximately the same time each day. To facilitate patient-completion of these PRO tools, a Nurse/Research Coordinator will contact each

patient each day (days 2-8) to remind the patient to complete forms, answer questions, and to query toxicities.

V. Statistical Considerations

This is a randomized, placebo-controlled, pilot study to determine the effect of olanzapine on chronic nausea and/or vomiting in cancer patients. Patients will be randomly assigned to receive either olanzapine or placebo at a 1:1 ratio and stratified based on gender. The primary endpoint is the change in nausea scores from baseline to 24 hours of treatment using the Visual Analogue Scale. Secondary endpoints include daily nausea and vomiting scores, daily episodes of vomiting/retching (number and time), the utilization of rescue therapy, and toxicities of olanzapine as measured by PRO questionnaires and CTCAE v4.0.

The primary objective of this pilot trial is to estimate the effect of olanzapine on chronic nausea and vomiting to inform future design of a randomized phase III clinical trial. Descriptive statistics and statistical plots will form the foundation of statistical analysis for this trial. We will summarize the study endpoints by mean (SD), median (inter-quartile range), and frequency (percentage). Nausea change scores will be compared between arms using a two-sample t-test or a Wilcoxon rank sum test as appropriate. If the two-sided p value is less than 0.05, then we will consider this to be supportive of a statistically significant advantage for olanzapine in this situation. If the p value is 0.2 or better, in the correct direction, then this would support further study in a larger phase III trial. The difference in nausea change scores from baseline to 24-hours post treatment between the two arms will be estimated along with a 95% confidence interval. We will plot the repeated measurements of nausea and vomiting longitudinally to explore the pattern over time and difference between treatment arms. Because of exploratory nature of this pilot study, we will not adjust for multiple comparisons. Due to the logistical and financial constraints, the total sample size will be fixed at 30 patients, 15 patients per arm. Assuming a 10% drop-out due to ineligible patients, cancellations, and major violations, we expect to have 13 patients per arm evaluable for the primary endpoint. As this is a pilot trial with a limited sample size with the primary goal of exploring the effect of olanzapine on nausea, no formal power analysis was conducted. Assuming an accrual rate of 3 patients per month, the patient accrual will be completed in 10 months, and analysis will be performed approximately 3 months following accrual completion.

VI. Investigator Roles

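### The primary test compares change scores without adjusting for baseline nausea or the gender stratum, which probably gives away some precision with about 26 evaluable patients

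*Combined protocol and SAP*

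**What the plan says.** V. Statistical Considerations defines the endpoint: "The primary endpoint is the change in nausea scores from baseline to 24 hours of treatment using the Visual Analogue Scale". The analysis follows: "Nausea change scores will be compared between arms using a two-sample t-test or a Wilcoxon rank sum test as appropriate". The between-arm difference in change is to be reported with a 95% confidence interval. Two thresholds apply to the p-value: two-sided 0.05 for a significant advantage, and a looser one for continuing: "If the p value is 0.2 or better, in the correct direction, then this would support further study in a larger phase III trial". The sample is fixed at 30, with 13 per arm expected to be evaluable, and no power calculation was made.

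Study Design and Treatment Regimen states "Randomization will be stratified by gender", and V. Statistical Considerations repeats it. No section names a model that includes gender or baseline nausea.

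Both variables are available before treatment. Gender is on the demographics form (Appendix I). For nausea, Data Collection and Forms says "The patient will complete the Baseline and Daily Questionnaire and Vomiting Assessment on day one prior to the start of treatment", and Study Visits and Assessment Procedures gives the measurement times as "day 1 pre-treatment and days 2-8 post treatment initiation".

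**The concern.** A t-test on change scores is the same as regressing the 24-hour score on arm with the baseline coefficient set to 1 instead of estimated. If the true slope is below 1, two things follow. The change score is noisier than it needs to be, and part of any chance baseline difference between arms passes into the estimated effect. Leaving out gender means that any variation it explains stays in the error term.

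The confidence interval and the p of 0.2 rule are the main quantitative results this pilot passes to a phase III decision. Because the sample size cannot grow, the choice of analysis is one of the few remaining ways to improve precision.

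**Working it through.** **The plan's own figure.** 15 x (1 - 0.10) = 13.5, rounded down to 13 per arm, 26 in total. This reproduces.

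**Inputs.** From the documents: 13 per arm, 1:1 allocation, gender as stratum, a 0 to 10 scale, and go if two-sided p is 0.2 or less in favour of olanzapine. Assumed, because the documents give none of them: SDs, the baseline-to-24-hour correlation r, and a true effect of 1.5 points.

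**Formulas.** With baseline SD s0 and 24-hour SD s1:

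- Change-score variance: s0² + s1² - 2·r·s0·s1, tested on 24 df (t = 2.064).
- Adjusted variance: s1²(1 - r²), times a small-sample factor 1 + 1/22, tested on 22 df (t = 2.074).
- CI half-width: t × sqrt(variance × 2/13).
- True slope: r·s1/s0. With equal SDs the variance ratio, adjusted to change, is (1 + r)/2 before the small-sample factor.

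**Worked case, equal SDs of 2.5, r = 0.5.**

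- Change: SD = 2.5 × sqrt(2 × 0.5) = 2.50; half-width = 2.064 × 2.50 × 0.392 = 2.02.
- Adjusted: SD = 2.5 × sqrt(0.75) = 2.165; half-width = 2.074 × 2.165 × 0.392 × sqrt(1 + 1/22) = 1.80.

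Simulation gives mean half-widths of 2.00 and 1.78. They are slightly lower because the estimated SD averages a little below the true one.

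**(1) Simulation, normal scores, equal SDs of 2.5** (20,000 trials per setting; change-score t-test against the model with baseline and gender):

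| r | Half-width, change | Half-width, adjusted | Go rate, change | Go rate, adjusted |
|---|---|---|---|---|
| 0.3 | 2.38 | 1.97 | 49% | 59% |
| 0.5 | 2.00 | 1.78 | 59% | 66% |
| 0.7 | 1.55 | 1.47 | 75% | 78% |
| 0.8 | 1.27 | 1.24 | 86% | 88% |
| 0.9 | 0.90 | 0.90 | 98% | 98% |

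With no true effect (10,000 trials per setting) both analyses meet the go rule about 10% of the time. Break-even with equal SDs is at r of about 0.89. At r = 0.5 the change-score test would need about 33 patients to match the adjusted analysis with 26.

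**(2) Bounded scores.** These are whole numbers from 0 to 10 with baseline at least 3, to mimic the nausea entry criterion (assumed latent mean 6, SD 2.5, 1-point placebo drop; 12,000 trials per setting):

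| r | Realised slope | Half-width, change | Half-width, adjusted | Go rate, change | Go rate, adjusted |
|---|---|---|---|---|---|
| 0.3 | 0.30 | 2.16 | 1.89 | 51% | 59% |
| 0.5 | 0.50 | 1.87 | 1.74 | 59% | 64% |
| 0.7 | 0.71 | 1.50 | 1.46 | 75% | 76% |
| 0.8 | 0.81 | 1.26 | 1.25 | 85% | 85% |
| 0.9 | 0.92 | 0.93 | 0.95 | 97% | 97% |

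False-go is 10 to 11% for both (6,000 trials per setting). The floor of 3 is not universal, because Eligibility Criteria also admits patients on vomiting alone. If 25% are assumed to enter that way with latent mean nausea 3, the half-width goes from 1.96 to 1.71 at r = 0.5 and from 0.97 to 0.94 at r = 0.9.

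**(3) Unfavourable cases: 24-hour scores more spread than baseline.**

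- SD 1.5 then 2.5, r = 0.6: slope = 0.6 × 2.5/1.5 = 1.0. Half-width 1.60 to 1.65, go rate 72% to 70%.
- SD 2.0 then 2.5, r = 0.8: slope = 0.8 × 2.5/2.0 = 1.0. Half-width 1.20 to 1.24, go rate 89% to 88%.

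**(4) Gender alone.** Adding gender to a model that already has baseline (r = 0.5) changes the half-width from 1.77 to 1.79 if gender is not prognostic, from 1.83 to 1.79 if it shifts the score by 1 point, and from 1.97 to 1.79 if by 2 points.

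**(5) Chance imbalance.** One standard error of the baseline difference is 2.5 × sqrt(2/13) = 0.98 points. It moves the change-score difference by (1 - slope) × 0.98: 0.49 at slope 0.5, 0.20 at slope 0.8, and 0 at slope 1.

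**The case against.** The planned test is not an error. It keeps its false-positive rate, it matches an endpoint defined as a change, and the section calls the trial exploratory with descriptive statistics as its foundation. The go rule supports further study but does not decide it alone. That limits the weight of the point, but the plan still attaches two p-value thresholds and a confidence interval to this comparison.

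Every size rests on assumed inputs, and the largest gains need r of 0.3 to 0.5. Entry requires nausea to be long-standing ("Have chronic nausea that has been present for at least one week") unless the patient qualifies on vomiting, and ratings are taken at about the same time each day, so a higher correlation is plausible. In a smaller simulation of bounded scores (2,500 trials per r), with gender neither prognostic nor balanced by arm, the half-width went from 1.50 to 1.49, 1.25 to 1.28 and 0.94 to 0.98 at r = 0.7, 0.8 and 0.9, but still fell from 1.87 to 1.77 at r = 0.5. This stands: the gain may be nil.

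The gender part is weak by itself. Nothing in the documents shows that gender predicts 24-hour nausea. Most of the gain comes from baseline; the case for gender is that it was stratified on and costs one degree of freedom.

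Only the t-test was simulated, so the comparison does not cover the Wilcoxon option. Keeping that test as a sensitivity analysis partly answers this.

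Finally, III. Study Objectives states a different primary aim, to "estimate the proportion of cancer patients with an improvement in chronic nausea". The endpoint has to be settled first, and the adjusted model applies only if the 24-hour score is kept.

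**Conclusion.** The concern holds as a point of efficiency, not validity. The primary comparison is unadjusted, it uses baseline only by subtraction, and it omits the one stratification factor.

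Under equal SDs of 2.5 and a 1.5-point effect, adjustment narrows the 95% CI by about 17%, 11% and 5% at correlations of 0.3, 0.5 and 0.7. It adds 10, 7 and 3 percentage points to the chance of a go. The trade is uneven: up to 0.41 points of half-width gained (2.38 - 1.97) against 0.04 to 0.05 lost in the unfavourable cases tested.

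A slope below 1 is likely but not shown in the documents, so confidence in a real gain is medium. The change is worth making because it is cheap and does not raise the false-go rate.

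**What to change.** In V. Statistical Considerations, make the primary analysis a linear model of the 24-hour nausea score on arm, baseline nausea and gender. Using the change score as the outcome in the same model gives the identical arm difference, so the endpoint can stay as worded. Report the adjusted difference, its 95% CI and p-value, and apply the 0.05 and 0.2 rules to that p-value. Keep the unadjusted t-test and the Wilcoxon test as named sensitivity analyses. If the sponsor settles on the proportion improved as primary, this model does not apply to it.

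The cost is SAP wording and two degrees of freedom, plus about 0.04 to 0.05 points of half-width if the true slope is near 1. No new data are needed.
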